10.3.2 Secondary Endpoints

Secondary endpoints (change in OI, P/F ratio, and pre- and post-ductal SpO₂, time on mechanical ventilation, and change in NT-proBNP) will be summarized and tested using group t-test. Kaplan-Meier estimate will be provided for time to event variables (time to discontinuation of iNO, time to initiation of ECMO, and time to clinical worsening) and log-rank test will be used to test the treatment differences.

Plasma samples will be analyzed for treprostinil using a validated bioanalytical plasma assay. Individual and mean treprostinil plasma concentration data, and treprostinil pharmacokinetic parameters, determined as able, will be summarized using descriptive statistics.

10.3.3 Safety Analyses

Safety of study drug in neonates will be evaluated by combined assessments of AEs, clinical laboratory parameters, vitals, and physical examination findings. All subjects who receive study drug will be included in the safety population. Statistical summaries of safety data will be

descriptive and exploratory in nature, focusing on the incidence of adverse experiences. The safety data collected in this study will be presented in listings and summary tables.

Treatment-emergent changes in vital signs, incidence of treatment-emergent AEs, and treatment-emergent changes in clinical laboratory parameters will be evaluated.

All AEs will be coded according to the Medical Dictionary for Regulatory Activities (MedDRA) dictionary. The incidence of AEs within each treatment group will be presented in summary tables overall, and by system organ class and preferred term.

Vital sign and clinical laboratory data collected prior to initiation of study drug will serve as Baseline values for evaluation of data collected during the treatment period. Summary statistics will be calculated for measured values at each time point assessed, as well as change from baseline values within each cohort.

No inferential statistical analyses are planned for safety data.

10.4 INTERIM ANALYSIS

A safety review will be conducted by a Data Safety Monitoring Board (DSMB) after the first 10 subjects have been randomized to receive study drug and have completed the 14-day study period. A second review will occur once 40 subjects have been enrolled and completed the 14-day study period. Ad hoc meetings may be scheduled at additional enrollment milestones or in response to events related to the safety of study treatment.

10.5 OTHER ANALYSES

Exploratory analyses may be conducted based on available study data, such as at additional time points and calculation of a Total Inotropic Dose Index with each dose change.

10.6 DATA LISTINGS AND SUMMARIES

The safety population will be used for all data listings, summaries and figures. All available data will be presented with no imputation for any missing data. Subjects will contribute the data available up to the point of study completion, or study discontinuation for any reason.

In general, listings will be sorted by subject, descriptive summaries will include number of observations (n), mean, standard deviation (SD), median, minimum, maximum for continuous variables and n and percent for categorical variables. For all continuous variable summaries, n, arithmetic mean, median, minimum, maximum, and SD will be provided.

Plasma concentration data and any applicable derived pharmacokinetic parameters will be summarized and displayed in both tabular and graphical form. Comparative plots of individual concentration data may be produced and summarized across subjects.

10.7 DATA SAFETY MONITORING BOARD (DSMB)

A DSMB will be established for the study, composed of up to four independent members including physicians knowledgeable in the treatment of PPHN and a statistician. The DSMB will meet to monitor the safety of the study as established in a DSMB charter.

11 PACKAGING AND FORMULATION

11.1 CONTENTS OF STUDY DRUG

United Therapeutics will supply study drug (Remodulin or matching placebo) for administration in the study. Study drug will be supplied in 20mL clear glass vials sealed with a rubber-coated stopper and fitted with a cap containing 20mg (1mg/mL) of treprostinil or placebo as sterile solutions in water for injection.

Remodulin Composition Description: 1mg/mL treprostinil. Each mL also contains 5.3mg sodium chloride, 3mg metacresol, 6.3mg sodium citrate, and water for injection. Sodium hydroxide and hydrochloric acid may be added to adjust pH between 6.0 and 7.2.

Placebo Component Description: Sodium Citrate USP/EP/JP, Sodium Chloride USP/EP/JP, Sodium Hydroxide Pellets, Metacresol, Citric Acid (anhydrous). Used to adjust pH, if needed: 1M Citric Acid, 1N NaOH.

11.2 LABELING

Each vial will be labeled in accordance with applicable national regulations, to include at least the following information: investigational product name, trial reference code, concentration, quantity, route of administration, manufacture or expiry date, lot number, Sponsor name, address and

telephone number, and storage conditions. The labels may include blank fields for sites to document the following information, including but not limited to, Investigator name, subject number/initials, and date the vial was opened.

11.3 STORAGE AND HANDLING OF STUDY DRUG

Study drug will be stored at a controlled temperature of 25°C (77°F) with excursions permitted to 15-30°C (59-86°F). Study drug vials should not be frozen or exposed to heat. Temperature excursions should be reported to United Therapeutics as soon as they are identified via email [REDACTED] and any affected drug should be quarantined until notified by the Sponsor. Study drug should not be used after the expiry date that is stated on the vial. The expiry date refers to the last day of that month. Study drug should not be used if any damage to the vial, discoloration, or other signs of deterioration is noticed. A study drug vial must be used or discarded within 30 days after initial puncture.

Study drug must be diluted to the appropriate concentration based upon the subject weight, dose and fluid constraints (i.e. flow rate) in this neonate patient population. Diluted study drug solution can be administered for up to 52 hours at 37°C when diluted to concentrations as low as 250ng/mL in 0.9% sodium chloride; although it is recommended to change the drug solution every 48 hours.

Selection of Diluent

Route	Diluent	Storage and Administration Limits
IV	Sterile Diluent for Remodulin ¹ Sterile Diluent for Flolan Sterile Diluent for Epoprostenol Sodium	Do not use beyond 16 days from date of preparation ² . Store at room temperature. Syringes may be administered up to 48 hours.
	Sterile water for injection 0.9% Sodium Chloride for Injection	Do not use beyond 52 hours from time of preparation if maintained at room temperature. Syringes may be administered up to 48 hours ³ . May be stored up to 24 hours in the refrigerator after preparation. May be administered up to 48 hours once removed from the refrigerator ³ .
SC	None	Do not use beyond 76 hours from time of preparation if maintained at room temperature. Syringes may be administered up to 72 hours. May be stored up to 24 hours in the refrigerator after preparation. May be administered up to 72 hours at 37°C once removed from the refrigerator.
	Sterile water for injection 0.9% Sodium Chloride for Injection	Do not use beyond 52 hours from time of preparation if maintained at room temperature. Syringes may be administered up to 48 hours ³ . May be stored up to 24 hours in the refrigerator after preparation. May be administered up to 48 hours once removed from the refrigerator ³ .

¹Sterile Diluent for Remodulin may be provided during the trial once available.

²Allows for multiple syringes to be prepared in advance for a subject.

³Studies have been performed with concentrations as low as 250ng/mL in 0.9% sodium chloride administered for up to 52 hours at 37°C; although it is recommended to change the drug solution at least every 48 hours.

Currently, there are no data to confirm whether Remodulin is compatible and may be administered in the same line/lumen with other IV administered agents; however, compatibility studies are planned. Therefore, until the Investigator is notified by United Therapeutics of the outcome of the compatibility studies, one line or lumen must be dedicated solely to study drug when administering as a continuous IV infusion.

All study drug must be accounted for and the Investigator will maintain a log sheet of all vials as they are received and used during the study. The pharmacist or appropriate personnel will retain all study drug used for each study subject.

11.4 SUPPLY AND RETURN OF CTM

Study sites will be supplied with a sufficient quantity of study drug to begin enrollment in the study. Appropriate arrangements will be made for resupply to the site with respect to subject enrollment.

All used and unused study drug should be retained by the pharmacist or appropriate personnel at the site (including empty, partially used and unopened vials).

11.5 DRUG ACCOUNTABILITY

The Investigator is responsible for study drug accountability and reconciliation overall and on a per subject basis. Drug accountability records are to be maintained during the study and these records include: the amount of study drug received from the Sponsor, the amount dispensed to each subject, and the amount of unused drug. The quantity of investigational product lost, missing, destroyed, etc. must also be accounted for and documented. At the end of the study, reconciling the delivery records with those of usage and discarded stocks must be possible. Accounts must be given of any discrepancies. Once a representative from the Sponsor is able to confirm drug accountability, study drug will be returned to a Sponsor-designated location for destruction.

12 REGULATORY AND ETHICAL OBLIGATION

12.1 U.S. FDA OR APPLICABLE REGULATORY REQUIREMENTS

The study will be conducted in accordance with ICH and GCP guidelines and all applicable national regulations. The Sponsor will obtain the required approval from each national regulatory authority to conduct the study. During the conduct of the study, an annual safety report will be compiled by the Sponsor for submission to those regulatory authorities and IRBs/ECs that require it. Any additional national reporting requirements as specified by the applicable regulations, regulatory authorities, or IRB/EC will also be fulfilled during the conduct of the study.

12.2 INFORMED CONSENT REQUIREMENTS

Before a subject is enrolled in the study, the Investigator or his/her designees must explain the purpose and nature of the study, including potential benefits and risks and all study procedures to the subject's parent(s) or legal guardian(s). The subject's parent(s) or legal guardian(s) must sign and date an IRB/EC-approved informed consent/parental permission form prior to the conduct of any study-related activities. A copy of the signed consent/parental permission form will be given to the subject's parent(s) or legal guardian(s) and the original will be retained in the study site's records.

12.3 INDEPENDENT ETHICS COMMITTEE/INSTITUTIONAL REVIEW BOARD

Prior to study initiation at each site, the Investigator will obtain approval for the study from an appropriate IRB/EC and provide the Sponsor with a copy of the approval letter. The IRB/EC must also review and approve the study site's informed consent form and any other written information provided to the subject prior to enrollment, as well as any advertising materials used for subject recruitment. Copies of the informed consent form and advertising materials must be forwarded to the Sponsor for review before submission to the IRB/EC prior to the start of the study.

If, during the study, it is necessary to amend either the protocol or the informed consent form, the Investigator is responsible for obtaining IRB/EC approval of these amended documents prior to implementation. Copies of the IRB/EC correspondence and approval letters must be provided to the Sponsor.

During the conduct of the study, an annual progress report will be compiled by the Sponsor for submission to those IRBs/ECs that require it.

A written summary of the study will be provided by the Investigator to the IRB/EC following study completion or termination according to their standard procedures. Additional updates will also be provided in accordance with the IRB/EC's standard procedures.

12.4 PRESTUDY DOCUMENTATION REQUIREMENTS

Before the commencement of the clinical trial, the following documents will be provided to the site: Investigator's Brochure, protocol, model informed consent form, budget, and clinical trial agreement.

The site will be required to provide the following documents to United Therapeutics Corporation or designee prior to study start: Investigator signature page of the protocol, Form FDA 1572, IRB/EC Composition and Roster, IRB/EC protocol and informed consent approval letters, Curriculum Vitae, financial disclosure forms of study staff listed on the Form FDA 1572, and an authorized clinical trial agreement.

12.5 SUBJECT CONFIDENTIALITY

Every effort will be made to keep medical information confidential. United Therapeutics Corporation and the agents of the Sponsor, the FDA or other regulatory bodies, and the IRB/EC governing this study may inspect the medical records of any subject involved in this study. The Investigator may release the subject's medical records to employees or agents of the Sponsor, the IRB/EC or the FDA or appropriate local regulatory agencies for purposes of checking the accuracy of the data. A number will be assigned to all subjects and any report published will not identify the subject's name.

13 ADMINISTRATIVE AND LEGAL OBLIGATIONS

It is understood that the term "Investigator" as used in this protocol and on case report forms refers to the Principal Investigator or a member of the staff that the Principal Investigator designates to perform a certain duty (as documented on the Delegation of Authority Log). The Principal Investigator is ultimately responsible for the conduct of all aspects of the study in accordance with the protocol, even those tasks delegated to others, and ensuring written informed consent is obtained from the parent(s) or legal guardian for each individual participating in this study.

13.1 PROTOCOL AMENDMENTS AND STUDY TERMINATION

Protocol amendments that could potentially adversely affect the safety of participating subjects or that alter the scope of the investigation, the scientific quality of the study, the experimental design, dosages, duration of therapy, assessment variables, the number of subjects treated, or subject selection criteria may be made only after consultation between United Therapeutics Corporation or its designee and the Investigator.

All protocol amendments must be submitted to and approved by the appropriate regulatory authorities and IRB/EC prior to implementation.

A report documenting study termination must also be submitted to and acknowledged by the appropriate IRB/EC for each study site, in accordance with IRB/EC policies.

At the end of the study, where applicable, a final report will be provided to the local regulatory agencies.

13.2 STUDY DOCUMENTATION AND STORAGE

In accordance with federal/national regulations, ICH, and GCP guidelines, the Investigator must retain study records for at least 2 years after the last approval of a marketing application in an ICH region and until there are no pending or contemplated marketing applications in an ICH region or at least 2 years have elapsed since the formal discontinuation of clinical development of the investigational product. Where required by other applicable regulatory requirements, the Investigator shall retain the documents for a longer period.

The Investigator must notify United Therapeutics Corporation in writing before any disposal or change in location of study records.

13.3 STUDY MONITORING AND DATA COLLECTION

In accordance with federal/national regulations, ICH, and GCP guidelines, monitors for United Therapeutics Corporation or its designee will periodically contact the site and conduct on-site visits. During these visits, the monitor will at a minimum: confirm ethical treatment of subjects, assess study progress, review data collected, conduct source document verification, verify drug accountability periodically, and identify any issues requiring resolution.

The Investigator agrees to allow the monitor direct access to all relevant documents and to allocate his/her time and his/her staff to the monitor to discuss any findings or any relevant issues.

15 APPENDICES

15.1 GUIDELINES AND DEFINITIONS FOR RECORDING ADVERSE EVENTS

For each adverse event, the Investigator will: (1) rate the intensity and seriousness of the AE, (2) estimate the causality of the AE to study drug, and (3) note actions taken to counteract the AE.

Definitions of Intensity, Seriousness, Causality, and Action Taken

Intensity

An assessment of the relative intensity (severity) of an AE is based on the investigator's clinical judgment. The maximum intensity encountered during the evaluation period should be checked. The assessment of intensity should be independent of the assessment of the seriousness of the AE.

- Mild: No limitation of usual activities.
- Moderate: Some limitation of usual activities.
- Severe: Inability to carry out usual activities.

Difference Between "Severe" and "Serious"

The term "severe" is often used to describe the intensity (severity) of a specific event (as in mild, moderate or severe myocardial infarction); the event itself; however, may be of relatively minor medical significance (such as severe headache). This is not the same as "serious", which is based on the outcome or action criteria usually associated with events that pose a threat to life or functioning. Seriousness (not severity) serves as a guide for defining regulatory reporting obligations.

Causality

An estimate of causality between a specified AE and the study drug is made by the Investigator.

Definitions of the categories follow:

- POSSIBLE - the AE MAY have been caused by study drug. There is a reasonable causal relationship between the study drug and the SAE. The event responds to dechallenge. Rechallenge is not required.
- PROBABLE - it is LIKELY that the AE was caused by study drug. There is a reasonable causal relationship between the study drug and the SAE. Dechallenge information is lacking or unclear.
- NOT RELATED - it is UNLIKELY that the AE was caused by study drug. There is not a temporal relationship to study drug administration (too early, or late, or study drug not

taken), or there is a reasonable causal relationship between another drug, or concurrent disease and the SAE.

Action Taken with Test Agent*

The action taken with test agent as a direct result of the AE:

- DOSE NOT CHANGED - there was no alteration in either the dose or regimen of the test agent
- DOSE INCREASED – dose was increased
- DOSE DECREASED – dose was decreased
- DRUG INTERRUPTED - the dose or regimen of the test agent was altered or administration of the test agent was stopped temporarily
- DRUG WITHDRAWN- administration of the test agent was stopped permanently and not restarted. This does not apply if the subject was on drug at the time of death. For this scenario “Dose not changed” would be marked.
- Not Applicable- (i.e., AE occurred prior to administration of test agent)

* Only the last action should be recorded on the CRF.

Outcome

- Fatal – The study subject died
- Not Recovered/Not Resolved – The AE was ongoing at the end of the study/AE observation period
- Recovered/Resolved – The AE resolved
- Recovered/Resolved with Sequelae – The AE is considered resolved; however, there is a residual sequelae
- Recovering/Resolving – The AE is improving but is not yet completely recovered/resolved at the end of study/AE observation period
- Unknown – The outcome of the AE cannot be determined

AE/SAE Start Date verses Serious Date

The AE start date is classified as the first day the subject experiences sign and symptoms of an event and should be entered on the eCRF and SAE Notification Form section “Onset date of symptoms.” The date the event became serious is the first day the event meet one of the serious criterion (see section 9.1.2). The start date and date event became serious could be the same date (e.g., clavicle fracture from a fall).

Note: The start date (onset) should never be a date prior to the subject signing the informed consent.

AE/SAE Stop Date

For AEs and SAEs the dates listed on the eCRF and SAE Notification Form will always be the same. For non-fatal events, this is the date the last sign and/or symptom resolved. For fatal events this is the date of Death. If the event Recovered/Resolved with Sequelae enter the date the subject's medical condition resolved or stabilized.

For SAEs follow-up must continue until resolution, death, end of study, or subject is lost to follow-up.

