8 STUDY TERMINATION

8.1 CRITERIA FOR SUBJECT WITHDRAWAL

A subject may be withdrawn from the study and/or study drug by the Investigator at any time for reasons including, but not limited to, the following:

- The subject's parent or legal guardian wishes to withdraw the subject from further participation.
- A serious or life-threatening AE occurs or the Investigator considers that it is necessary to discontinue study drug to protect the safety of the subject.
- The subject did not initiate study drug.

If a subject is discontinued from the study prematurely, the Investigator must complete all applicable eCRF records, including the End of Study Record for that subject. If study drug has been administered, the Investigator should make every effort to perform all scheduled evaluations. In the event that a subject discontinues study drug prematurely due to an AE, the subject will be followed until either the Investigator determines that the AE has resolved, it is no longer considered clinically significant, the subject is lost to further follow-up, or for 4 weeks after last dose of study drug.

SAEs will be followed by United Therapeutics Corporation Global Drug Safety until resolution, death, or the subject is lost to follow-up.

If withdrawal from study drug is warranted, the dose of study drug will be weaned until discontinued. Abrupt cessation of study drug will be avoided due to the risk of rebound pulmonary hypertension.

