9.5 SAFETY REPORTS

In accordance with FDA, European, and national regulations, the Sponsor will notify the FDA, other competent authorities, and all participating Investigators of any AE that is considered to be possibly attributable to study drug and is both serious and unexpected. The Investigator must report these AEs to their IRB or EC in accordance with applicable national regulations and guidelines set forth by the IRB or EC.

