12.2 ADVERSE EVENTS

All AEs will be coded to PT and SOC using the latest version of the MedDRA coding dictionary. Treatment-emergent adverse events (TEAEs) are those AEs with onset date equal to or after the start date of the study drug. TEAEs will appear in listings and summaries. Non-treatment-emergent AEs (the AEs occurring after signing the Informed Consent Form (ICF), but before receiving study drug) will be listed, but will not be included in summary tables.

The AE listings will include the AE verbatim term and its corresponding PT and SOC, all eCRF details, and a treatment-emergent indicator flag. The following AE listings will be provided:

- All AEs
- Deaths
- SAEs
- AEs leading to permanent discontinuation of study drug

All AE summaries will be sorted by overall frequency and/or SOC and will include the number and percentage of subjects experiencing each type of AE, the total number of each type of AE, and the AE rate of each type of AE. AE rate will be calculated as the total number of AEs divided by the total patient days of exposure to study drug per treatment group.

The following AE summaries will be provided:

- AEs by SOC and PT
- AEs by PT
- Deaths
- SAEs by SOC and PT
- Non-serious AEs by SOC and PT
- AEs probably or possibly related to study drug by SOC and PT
- AEs leading to permanent discontinuation by PT
- AEs by SOC, PT, and severity (mild, moderate, severe)

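### Protocol 15.1 ties dechallenge evidence to the wrong causality labels and gives no related category to an AE that clearly persists after study drug is stopped

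*Protocol*

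**What the plan says.** Protocol 15.1, under Causality, gives three categories.

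- POSSIBLE: "the AE MAY have been caused by study drug". It requires a reasonable causal relationship and adds "The event responds to dechallenge. Rechallenge is not required".
- PROBABLE: "it is LIKELY that the AE was caused by study drug". It carries the same causal sentence and adds "Dechallenge information is lacking or unclear".
- NOT RELATED: causation is unlikely. Either "There is not a temporal relationship to study drug administration", or another drug or a concurrent disease offers a reasonable causal explanation.

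Each definition opens by speaking of the AE and then speaks of the SAE, although all AEs are rated. The same appendix has an outcome code for events that have not resolved, so persistence is foreseen.

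The ratings feed one planned summary: "AEs probably or possibly related to study drug by SOC and PT" (SAP 12.2, Table 14.3.1.7). Protocol 9.1.3 separately defines a suspected adverse reaction by a reasonable possibility of causation and sets no dechallenge condition. Protocol 9.5 has the sponsor notify authorities and investigators of "any AE that is considered to be possibly attributable to study drug and is both serious and unexpected".

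**The concern.** POSSIBLE and PROBABLE share the same causal sentence, so dechallenge is the only evidence criterion that separates them. It points the wrong way: recovery off drug earns MAY, and missing information earns LIKELY. The protocol's own words show this, without reference to any outside causality scale.

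The second problem is an omission. An event can respond to dechallenge, be untested or unclear, or clearly fail to respond. The two related categories cover only the first two. A plausible AE that clearly continues after the drug is stopped has no related category.

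At stake are the meaning of individual ratings in listings and SAE reports, the completeness of the related-AE table, and agreement in coding across the roughly 40 planned centers (Protocol 3.4). Safety is part of the primary objective, and Protocol 10.3.3 plans no inferential safety analysis, so the descriptive tables carry the safety message.

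**Working it through.** The plan states no figure on this point, so there is none to reproduce. The check applies the three definitions to every combination of three inputs: dechallenge (positive; lacking or unclear; negative), a temporal link (yes or no), and a plausible other cause (yes or no). That gives 3 × 2 × 2 = 12 cases. Where there is a temporal link, a reasonable causal relationship is taken as given.

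| Temporal link | Other cause | Positive | Lacking or unclear | Negative |
|---|---|---|---|---|
| Yes | No | POSSIBLE | PROBABLE | none fits |
| Yes | Yes | POSSIBLE or NOT RELATED | PROBABLE or NOT RELATED | NOT RELATED only |
| No | No | NOT RELATED | NOT RELATED | NOT RELATED |
| No | Yes | NOT RELATED | NOT RELATED | NOT RELATED |

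1. **Reversal.** In the first row, positive dechallenge gives the weaker label and absent information the stronger one.
2. **Gap.** Negative dechallenge meets a related category in 0 of 4 cases. The two without a temporal link are properly NOT RELATED. The two with a link are the defect: one is unclassifiable, and the other can only be NOT RELATED.
3. **Availability of another cause.** Protocol Table 9-1 lists 21 events attributed to PPHN, including shock, coagulopathy and respiratory failure. A concurrent-disease explanation will often be at hand, so the second row is a realistic one.
4. **Effect of the reversal on the planned summary.** The table counts PROBABLE plus POSSIBLE. Exchanging the labels leaves that sum the same, so the change is 0.
5. **Effect of the gap on the planned summary.** Protocol 10.2 plans 33 evaluable infants per group. If one treprostinil infant's only related AE falls out, overall related-AE incidence drops by 1/33 = 0.030, about 3 percentage points. With 70 randomized 1:1 the group is 35, and 1/35 = 0.029. An infant with another AE rated related contributes nothing to this change, though the event count falls by one.

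The documents give no frequency of clearly negative dechallenge, so the total effect cannot be derived.

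**The case against.** The strongest reply is that little follows from a drafting slip. Most of the limits it sets are right.

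- Pooling means that the reversal alters no planned summary. This stands.
- A reader might infer that lasting harms default to NOT RELATED. The protocol has no such rule. NOT RELATED has its own conditions, and persistence meets neither. The concurrent-disease route to NOT RELATED is also open when dechallenge is positive or missing, so the gap does not create it.
- A reader might infer that irreversible harms as a class are lost. An intracranial bleed would not be expected to reverse when a drug stops, so its dechallenge is uninformative and can be read as unclear, which gives PROBABLE. A death on drug has no dechallenge and can be read the same way. Clean dechallenge will often be missing in any case, because "Abrupt cessation of study drug will be avoided due to the risk of rebound pulmonary hypertension".
- A reader might infer that serious events escape reporting. Protocol 9.4 sends every SAE to the sponsor whatever its causality, 9.1.3 sets no dechallenge condition, and 9.5 does not cite 15.1.
- A reader might infer that the ratings on file are inverted. Each definition opens with plain words for likelihood, and the documents do not show how sites resolved the conflict.
- SAP 12.2 also summarises all treatment-emergent AEs, SAEs and deaths by arm regardless of causality. In a placebo-controlled trial that comparison is the main safety evidence.

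What survives is narrower: the rule is wrong as written, and a potentially reversible AE that clearly does not resolve after stopping has no related category. Two investigators could reasonably code such an event differently.

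**Conclusion.** The point holds, with limited consequences. Under a literal reading, 15.1 inverts the strength of individual related ratings, with no effect on the pooled summary. The missing negative-dechallenge category can move events across the line between related and not related in one descriptive table. The size is up to 1/33 per treprostinil infant with no other related AE, in a number of infants that the documents do not allow one to estimate. It also makes coding inconsistent between sites.

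This rests on two assumptions: that investigators apply the dechallenge sentences as written, and that some AEs have a clear non-response after stopping. SAE reporting to the sponsor and the all-causality AE, SAE and death summaries are not affected. The correction is worth making because this is an operative rating rule and the change is cheap.

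**What to change.** In Protocol 15.1 and any eCRF guidance that repeats it:

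1. Define PROBABLE as a reasonable causal relationship with positive dechallenge, rechallenge not required.
2. Define POSSIBLE as a reasonable causal relationship with dechallenge lacking, unclear, not informative or negative, and state that non-resolution after stopping does not by itself exclude a related rating. Exchanging the two sentences alone would leave the gap open, so negative dechallenge must be named.
3. Write AE in place of SAE in all three definitions.
4. Align 15.1 with the reasonable-possibility standard in 9.1.3, and say which of the two governs attribution under 9.5.
5. Before database lock, make a blinded check of causality ratings for AEs not recovered after drug withdrawal, querying the investigator where the rating may have turned on the old wording.

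The cost is appendix wording, a site memo and a one-time blinded query on what should be a small set of ratings. No efficacy analysis, dosing or design element changes.
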